11.6 Dilated Ophthalmoscopy Outcomes

The number and percentage of subjects within each category of each dilated ophthalmoscopy outcomes will be summarized by visit, by eye and by treatment. Shift from baseline will also be evaluated.

The categories for the Shift from baseline for 'Vitreous', 'Macula', 'Peripheral retina', 'Choroid' and 'Optic nerve' assessments are defined as follow:

- Normal/clinically insignificant abnormality at Baseline to normal/clinically insignificant abnormality
- Normal/clinically insignificant abnormality at Baseline to clinically significant abnormality
- Clinically significant abnormality at Baseline to normal/Clinically insignificant abnormality
- Clinically significant abnormality at Baseline to clinically significant abnormality

The categories for the Shift from Baseline for 'Retinal tear(s)' and 'Retinal detachment' assessments are defined as follow:

- Absent at Baseline to absent
- Absent at Baseline to present
- Present at Baseline to absent
- Present at Baseline to present

11.7 Fundus Photography

Presence and severity of retinal pigment epithelium (RPE) hyperplasia, retinal arteriolar narrowing, retinal vessel sheathing, optic atrophy/pallor and optic disc swelling and presence of TOF will be analysed.

The categories for the Shift from Baseline are defined as follow:

- Absent at Baseline to absent
- Absent at Baseline to present
- Present at Baseline to absent
- Present at Baseline to present

Where absent corresponds to none and present to mild, moderate or severe.

The images quality will be summarized by visit and eye, by treatment and overall, based on counts and percentages. This includes image completeness, focus/clarity, field definition, stereopsis, exposure and contrast.

11.8 Immunogenicity Findings

Immunogenicity analyses will be performed on the Immunogenicity Population. Three immunogenicity assays will be analyzed: Anti-Drug Antibodies (ADA), Neutralizing timrepigene emparvovec antibodies (Nabs) and ELISpot.

In ELISpot data, a subject will be tested by 4 different analytes (REP1 Pool 1, REP1 Pool 2, REP2 Pool 3, AAV2) at each visit. All 4 analytes together are used to evaluate the immune response of the whole therapeutical product of BIIB111, in which, the 3 REP1 analytes are used to evaluate the immune response of the therapeutical gene, and the AAV2 analyte is used to evaluate the immune response of the transporting gene. A subject will be determined to have a positive result if any of the 4 analytes is positive at that visit. A subject will be determined to have a positive result with respect to the REP1 if any of the 3 REP1 analyte is positive at that visit. A subject will be determined to have a positive result with respect to the REP1 if any of the 3 REP1 analyte is positive at that visit. A subject will be determined to have a positive result with respect to the REP1 if any of the 3 REP1 analyte is positive at that visit. A Subject will be determined to have a positive result with respect to the REP1 if any of the 3 REP1 analyte is positive at that visit. A Subject will be determined to have a positive result with respect to the XAV2 if the AVV2 analyte is positive at that visit.

Baseline Definition

The baseline value for the immunogenicity assays is defined as the last available value prior to surgery of the study eye (or the study visit 2 Telephone Call for Control subjects). For subjects without any assessments prior to surgery of the study eye (low dose and high dose treatment groups), Day 1 sample will be used as baseline.

Assay Positivity by Visit

The number and percentage of subjects with positive results at any visit will be presented by baseline status (positive/negative) and by treatment group. Samples with a numeric titre is considered as positive. The positivity analysis for ELISpot will be summarized for the overall treatment of BIIB111 as well as with respect to either REP1 or AAV2.

Assay Treatment-Emergent Analysis by Visit

The number and percentage of subjects with a treatment-emergent positive result will be presented by visit and by treatment group. The treatment-emergent analysis for ELISpot will be summarized for the overall treatment of BIIB111 as well as with respect to either REP1 or AAV2.

A treatment-emergent positive result is defined as follow for ADA and Nabs:

• A post-baseline result that is positive when the baseline result is negative.

• A post-baseline result that has a titer greater than or equal to 4 times the baseline titer when the baseline result is positive, while titer values are available at both baseline and post-baseline visits.

For ELISpot, the treatment-emergent positive for each analyte is defined as a post-baseline result that is positive when the baseline result is negative. If any of the 3 REP1 analytes is treatment-emergent positive, it is a treatment-emergent positive for REP1. The treatment-emergent positive for AAV2 is defined as a post-baseline result that is positive when the baseline result is negative. If either REP1 or AAV2 is treatment-emergent positive, it is a treatment-emergent positive for the overall treatment of BIIB111.

If either valid baseline samples (see definition above, prior to surgery or Day 1) or valid postbaseline samples at a particular visit are not available, the subject will be assigned as missing for treatment-emergent status at that particular visit and excluded from the treatmentemergent assessment. The remaining available post-baseline assessments will be tabulated and will contribute to the positive/negative overtime summary. Invalid sample results include, but are not limited to "Quantify Not Sufficient", "No Results", "Pending Reassay Selection".

Relationship Between Immunogenicity Assay and Safety

The relationship between the immunogenicity assays (ADA, Nab and ELISpot) and selected adverse events will be assessed. These adverse events include ocular inflammation-related adverse events, visual acuity reduced-related adverse events and hypersensitivity-related adverse events. The number and percentage of post-treatment (treatment-emergent) ocular inflammation-related adverse events, visual acuity reduced-related adverse events and hypersensitivity-related adverse events (based on the adverse event data), as well as the number and percentage of eyes with a decrease from baseline of \geq 15 letters in BCVA at Month 12 (based on the visual acuity assessment data) will be summarized by (1) subjects with negative assay at baseline and subjects with positive assay at baseline; and (2) subjects with no treatment-emergent positive assay at any visit during the study and subjects with no treatment-emergent positive assay during the study. For ELISpot, the relationship with the selected adverse events will be summarized for the overall treatment of BIIB111 as well as with respect to either REP1 or AAV2.

The analyses will be conducted by treatment group and by eye. It will be repeated by AE severity (mild, moderate and severe) and by AE time to onset (\leq 30 days and >30 days post surgery). If an AE has more than one occurrence with an onset \leq 30 days and another >30 days, the AE will be reported in both \leq 30 days and >30 days time to onset categories.

Listings

Individual subject data will be listed with their positive/negative status, titer information (spot forming units (SFU) for ELISpot assay) and AEs of interests (as mentioned above) where available. The impact of assay status (positive/negative, treatment-emergent positive yes/no) on clinical efficacy may be further evaluated if needed.

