10.3 Visit 3 (Day 1 Post-Operative Visit)

At Visit 3 (Day 1), subjects in the AAV2-REP1 groups will return to the surgical site for a post-operative visit. The following assessments will be performed:

• Vital signs

- Immunoassay sampling (ELISA and cell-based assays only)
- BCVA
- Full ophthalmic examination, including IOP, a slit-lamp examination, lens opacity, and dilated fundus examination
- SD-OCT
- AE/SAE monitoring
- Concomitant medication, procedures, and treatment review
- Corticosteroid compliance review

Subjects will be reminded of the requirement to use barrier contraception for a period of 3 months from the time of treatment.

Subjects in the Control group will receive the Visit 3 Telephone Call at the agreed upon date and time. Sites will conduct the following assessments during the telephone call:

- AE/SAE monitoring
- Concomitant medication, procedures, and treatment review

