17 APPENDICES

17.1 Schedule of Study Procedures

Table 3 presents a schedule of study procedures.

Table 3 Schedule of Study Procedures

| Visit | Visit 1 ^a | Visit 2 ^b | Visit 3 ^b | Visit 4 ^b | Visit 5ª | Visit 6 ^ª | Visit 7ª | Visit 8 ^{a, c} | Early Termination ^d | Unscheduled Visit ^e |
|--|-------------------------------------|---------------------------|----------------------|--------------------------|-----------------|----------------------|---------------------|-------------------------|-----------------------------------|-----------------------------------|
| Study Day/Visit Window | Screening/ Baseline ^f | Day 0 Injection Day | Day 1 Post op | Day 7 Post op ± 3d | Month 1 ± 7d | Month 4 ±7d | Month 8 ± 14d | Month 12 ± 14d | | |
| Informed Consent | Х | | | | | | | | | |
| Demographics, medical and ocular history | Х | | | | | | | | | |
| Immunoassay blood sampling (ELISA and cell-based methods) ^g | х | | Х | х | Х | х | Х | х | х | |
| Immunoassay blood sampling (ELISPOT) ^g | Х | | | Х | Х | Х | Х | Х | х | |
| VFQ-25 ^h | Х | | | | | | | Х | Х | |
| Vital Signs | Х | | Х | Х | Х | | | Х | Х | |
| Weight ⁱ | Х | | | | | | | | | |
| | | | | | | | | | | |
| BCVA ^k | Х | | Х | Х | х | Х | Х | Х | Х | Х |
| Full ophthalmic exam ^l | Х | Х | Х | Х | х | Х | Х | х | Х | Х |
| SD-OCT | Х | | Х | Х | х | Х | Х | Х | х | х |
| Autofluorescence | Х | | | Х | Х | Х | Х | Х | Х | Х |
| Microperimetry | Х | | | | Х | Х | Х | Х | Х | |
| Contrast sensitivity ^m | Х | | | | | Х | Х | Х | Х | |
| Colour vision | Х | | | | | Х | Х | Х | Х | |
| 7-field colour fundus photos ⁿ | Х | | | | | | | Х | Х | |
| Reading speed test ^o | Х | | | | | | | Х | Х | |
| Randomisation | Х | | | | | | | | | |
| Corticosteroid dispensation/accountability ^p | Х | Х | Х | Х | Х | | | | | |
| Study drug/sub-retinal injection/vitrectomy/ retinal detachment | | X ^r | | | | | | | | |
| AE/SAE monitoring ^q | Х | Х | Х | Х | Х | Х | Х | Х | х | Х |

| Visit | Visit 1 ^a | Visit 2 ^b | Visit 3 ^b | Visit 4 ^b | Visit 5 ^ª | Visit 6 ^a | Visit 7 ^ª | Visit 8 ^{a, c} | Early Termination ^d | Unscheduled Visit ^e |
|---|-------------------------------------|---------------------------|----------------------|--------------------------|----------------------|----------------------|----------------------|-------------------------|-----------------------------------|-----------------------------------|

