3.5 Study Masking

Randomization of subjects aims to minimize potential selection bias.

Given a double-masked design is not feasible (i.e. treatment involves invasive surgical procedure under general anesthesia), the sponsor, investigator and the subject will be unmasked to whether a subject has been assigned to the timrepigene emparvovec treatment groups, or the untreated Control group. However, within the treated groups, the sponsor, investigator and subject will be masked to the assigned dose $(1.0 \times 10^{11} \text{ vg or } 1.0 \times 10^{10} \text{ vg})$. To further minimize potential performance/detection bias, all subjective ophthalmic assessments at the Screening/Baseline Period (Visit 1) and from Month 1 (Visit 5) onwards, will be conducted by a masked (outcomes) assessor.

Additional measures to minimize potential performance/detection bias include standardized methodologies across participating sites (same equipment, assessor training/certification, surgical training), and an identical visit/assessment schedule for treated/untreated patients.

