14.2 Appendix 2: Schedule of Study Procedures

Visit	Visit 1ª	Visit 2 ^b	Visit 3 ^b	Visit 4 ^b	Visit 5ª	Visit 6ª	Visit 7ª	Visit 8 ^{a, c}	Early Termination ^d	Unscheduled Visit ^e
Study Day/Visit Window	Screening/ Baseline ^f	Day 0 Injection Day	Day 1 Post op	Day 7 Post op ± 3d	Month 1 ± 7d	Month 4 ± 7d	Month 8 ± 14d	Month 12 ± 14d		
Informed Consent	X									
Demographics, medical and ocular history	Х									
Immunoassay blood sampling (ELISA and cell-based methods) ^g	х		x	x	x	x	x	x	х	
Immunoassay blood sampling (ELISPOT) ^g	Х		X	х	X	X	X	X	Х	
VFQ-25 ^h	Х							X	X	
Vital Signs	Х		X	X	X			X	X	
Weight ⁱ	X									
1										
BCVA ^k	Х		X	X	X	X	X	X	X	Х
Full ophthalmic exam ¹	X	X	X	x	X	X	X	X	X	х
SD-OCT	X		X	X	X	X	X	X	X	Х
Autofluorescence	Х			X	X	X	X	X	X	Х
Microperimetry	Х				X	X	X	X	х	
Contrast sensitivity ^m	Х					X	X	X	Х	
Colour vision	Х					X	Х	X	X	
7-field colour fundus photos ⁿ	Х							X	X	
Reading speed test ^o	X							X	X	
Randomisation	X									
Corticosteroid dispensation/accountability ^p	X	X	Х	Х	Х					

CONFIDENTIAL

Page 38 of 46

Biogen /	NightstarRx,	Ltd
BIIB111		

Visit	Visit 1ª	Visit 2 ^b	Visit 3 ^b	Visit 4 ^b	Visit 5ª	Visit 6ª	Visit 7ª	Visit 8 ^{a, c}	Early Termination ^d	Unscheduled Visit ^e
Study Day/Visit Window	Screening/ Baseline ^f	Day 0 Injection Day	Day 1 Post op	Day 7 Post op ± 3d	Month 1 ± 7d	Month 4 ± 7d	Month 8 ± 14d	Month 12 ± 14d		
Study drug/sub-retinal injection/vitrectomy/ retinal detachment		Xr								
AE/SAE monitoring ^q	Х	Х	X	X	X	Х	X	X	X	х
Concomitant medication, procedures and treatment review	х	х	х	х	х	х	х	х	х	х

Abbreviations: AE=adverse event; BCVA=best corrected visual acuity; ELISA=enzyme-linked immunosorbent assay: ELISPOT=enzyme-linked immunospot; ET=early termination; IOP=intraocular pressure; SAE=serious adverse event; SD-OCT=spectral domain optical coherence tomography; VFQ-25=25-item Visual Function Ouestionnaire.

NOTE: An attempt should be made to perform all procedures in both eyes, unless otherwise specified. Each eye should be tested separately. If the subject is unable to complete a procedure due to poor vision in either eye, this should be documented in the source notes and the assessment not completed for that eye.

Assessments with gray shading are to be assessor-masked.

- ^a Visit may be performed over 2 consecutive days if necessary.

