- ^b Study Visits 2, 3, and 4 only apply to subjects in the AAV2-REP1 groups. For subjects in the Control group, a telephone contact will be made at Visits 2, 3, and 4, and information regarding AEs/SAEs and concomitant medications, procedures, and treatments will be recorded.
- c End of Study Visit.
- ^d An ET visit should be performed if a subject discontinues at any time.
- e If clinically indicated, subjects may need to return to the site for an unscheduled visit. At a minimum, all assessments listed will be performed.
- ^f Informed consent must be signed within 12 weeks prior of dosing (Visit 2). The Screening/Baseline Visit must be performed within 8 weeks of dosing (Visit 2). Assessments and procedures conducted in the final visit of the NIGHT study (including the ET Visit) may be used for the Screening/Baseline Visit if the final NIGHT study occurs within 8 weeks prior to dosing (Visit 2).
- ^g Samples will be taken and retained for analyses, if necessary.
- ^h VFQ-25: to be completed only at sites where a validated translation is available. VFQ-25 must be completed by subjects at the beginning of the study visit, before any significant interaction with the study staff.
- ⁱ Weight is assessed for dose calculation for 21-day corticosteroid regimen.

Ι....

^k In order to capture accurate BCVA values at Visit 1 (Screening/Baseline), the following conditions apply to the BCVA assessment:

CONFIDENTIAL

DocuSign Envelope ID: 9EEC395C-0D7A-4605-B5D7-D5DF30B311BC

Biogen / NightstarRx, Ltd	Statistical Analysis Plan: 273CH301 / NSR-REP-01
BIIB111	11FEB2021

If the BCVA value at Visit 1 (Screening/Baseline) is $\geq \pm 10$ letter gain or loss in the study eye compared to the previous NIGHT study visit (if applicable), then BCVA must be repeated an additional 2 times, resulting in a total of 3 BCVA measures at Visit 1. To facilitate the additional BCVA measures this visit should be conducted over 2 days, with BCVA measured twice on Day 1 and once on Day 2. All 3 BCVA values must be recorded in the eCRF. The highest score will be used to define subject eligibility.

If the BCVA value at Visit 1 (Screening/Baseline) is $\leq \pm$ 10-letter difference in the study eye compared to the previous NIGHT study visit (if applicable), then BCVA will be collected once and will not be repeated.

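### Any-visit antibody positivity is shown by arm although treated subjects have six scheduled post-baseline samples and controls four, so at equal background rates the control percentage can only be equal or lower

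*SAP*

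**What the plan says.** **The summary.** Under the SAP 11.8 subsection on positivity, for ADA, Nab and ELISpot: "The number and percentage of subjects with positive results at any visit will be presented by baseline status (positive/negative) and by treatment group". Nothing restricts this to visits common to all arms.

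**The sampling schedule.** Protocol Table 3 (section 17.1) and SAP Appendix 2 both mark the row "Immunoassay blood sampling (ELISA and cell-based methods" at Visit 1, at Visits 3 to 8 and at early termination. Protocol 10.3 limits the Day 1 draw: "Immunoassay sampling (ELISA and cell-based assays only". Protocol Table 3 accordingly has no ELISpot mark at Visit 3. SAP Appendix 2, in the row "Immunoassay blood sampling (ELISPOT", does have one.

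**The control arm.** Footnote b of the schedule says: "Study Visits 2, 3, and 4 only apply to subjects in the AAV2-REP1 groups". For controls, "a telephone contact will be made at Visits 2, 3, and 4", and only adverse events and concomitant medications, procedures and treatments are recorded. No blood can be drawn.

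**Related text.** SAP 11.8 lets the Day 1 sample stand in as baseline for treated subjects with no pre-surgery assessment, for the immunogenicity assays in general. SAP 3.5 lists, among the measures against bias, "an identical visit/assessment schedule for treated/untreated patients".

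**The concern.** A subject counts as positive in an any-visit summary if at least one sample is positive, so the percentage rises with the number of samples whenever some positives are isolated or intermittent. Treated subjects have two more scheduled antibody draws than controls, half as many again. A reader who sees the three arms side by side will naturally take the control column as the level to expect without vector. Part of any excess in the treated columns could then come from the extra Day 1 and Day 7 samples and not from a response to the product.

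What is at stake is how one descriptive immunogenicity table is read. No efficacy result depends on it.

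**Working it through.** The plan gives no figure for background assay positivity, so there is nothing to reproduce. The sample counts come from the documents; the rates and correlations below are assumptions.

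**Step 1. Scheduled post-baseline samples per subject.** Visit 1 is sampled in every arm, so only later draws differ. ELISA and cell-based sampling is taken to be the source of ADA and Nab results (Protocol 12.5.1 assigns antibody responses to these methods).

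| Assay and source | Treated | Control |
|---|---|---|
| ADA/Nab, both schedules | Day 1, Day 7, Months 1, 4, 8, 12: 6 | Months 1, 4, 8, 12: 4 |
| ELISpot, Protocol 10.3 and Table 3 | Day 7, Months 1, 4, 8, 12: 5 | 4 |
| ELISpot, SAP Appendix 2 | Day 1, Day 7, Months 1, 4, 8, 12: 6 | 4 |

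**Step 2. Independent samples.** With per-sample positive rate p, equal in all arms, and k samples, P(any positive) = 1 − (1 − p)^k. For example, at p = 5%: 1 − 0.95^4 = 18.5% and 1 − 0.95^6 = 26.5%.

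| Assumed p | k = 4 | k = 5 | k = 6 | Gap, 6 v 4 (from unrounded values) |
|---|---|---|---|---|
| 1% | 3.9% | 4.9% | 5.9% | 1.9 points |
| 2% | 7.8% | 9.6% | 11.4% | 3.7 points |
| 5% | 18.5% | 22.6% | 26.5% | 7.9 points |

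For ELISpot under the protocol (5 v 4), the gap at p = 5% is 22.6 − 18.5 = 4.1 points.

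**Step 3. Correlated samples.** Results from one subject are unlikely to be independent. Under a beta-binomial model with within-subject correlation ρ, set a = p(1/ρ − 1) and b = (1 − p)(1/ρ − 1). Then P(any positive) = 1 − B(a, b + k)/B(a, b), where B is the beta function. At p = 5%:

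| ρ | k = 4 | k = 6 | Gap |
|---|---|---|---|
| 0 | 18.5% | 26.5% | 7.9 points |
| 0.3 | 12.7% | 15.7% | 3.0 points |
| 0.6 | 8.9% | 10.1% | 1.2 points |
| 0.9 | 5.9% | 6.1% | 0.2 points |
| 1 | 5.0% | 5.0% | 0 |

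The expected control rate is never above the treated rate under equal p. The two coincide when positivity is fully persistent.

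**Step 4. After restriction to shared visits.** With Months 1, 4, 8 and 12 only, k = 4 in every arm. The gap due to the number of scheduled samples is then 0 for every p and ρ.

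**The case against.** **It is descriptive.** SAP 11 and Protocol 13.7 rule out significance testing for safety. SAP 11.8 only presents percentages, and nowhere is the control rate called background or subtracted. This stands. A reader might infer that the plan formally compares the arms against a control background, but the documents do not say so. Showing the percentages by arm invites that use without prescribing it.

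**The phrase may mean each visit.** The sentence sits under a heading about positivity by visit, and a later paragraph mentions an over-time summary. On that reading there is no problem. It is the less natural reading: for treatment-emergent results the same section says by visit outright, and its safety subsection uses any visit in the whole-study sense. The ambiguity is itself a reason to settle the wording.

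**A like-for-like view already exists.** Treatment-emergent positivity is presented by visit and arm, so Months 1 to 12 can be compared directly. This stands and limits the harm, but it does not correct the any-visit table.

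**The counts are scheduled draws.** Protocol 12.5.1 does not commit to assaying every sample, a Day 1 fallback baseline removes one treated sample, and an early termination visit may add one. This also stands, so 6 v 4 is the planned imbalance and the realised one may differ.

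**The tables relating assay status to adverse events.** A reader might infer that the imbalance carries into the inflammation and vision-loss tables. The documents do not support that. Those tables group subjects by baseline status and by treatment-emergent status, a different variable, and are produced within treatment group, where the planned schedule is the same for everyone. Dropping Day 1 and Day 7 there would only misclassify early responders.

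**The identical-schedule statement.** Taken alone it is contradicted by the telephone visits. However, Protocol 9.6.1 states and justifies that controls do not attend Visits 2 to 4, so nothing is concealed and no result changes.

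**Conclusion.** The point holds as a minor one. The any-visit summary in SAP 11.8 gives treated subjects more scheduled chances to be positive than controls: 6 v 4 for ADA and Nab, and 5 v 4 or 6 v 4 for ELISpot depending on the document. With equal per-sample background rates, the expected control percentage is equal or lower for schedule reasons alone.

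For the 6 v 4 schedule, the gap is about 2 to 8 points at assumed rates of 1% to 5% with independent samples. At 5% it falls to about 3 points at correlation 0.3 and to 0 at correlation 1. Neither the rate nor the correlation is in the documents, so the size is illustrative. It would be too strong to say that the control rate must be lower: where positivity is persistent the gap vanishes, and the split by baseline status separates subjects already positive at entry.

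The effect is confined to a descriptive safety table. The primary and key secondary analyses are untouched. The Day 1 ELISpot mismatch is a separate reconciliation point. ELISpot is scheduled for everyone at Visit 1, and SAP 11.8 sets treatment-emergent status to missing when no valid baseline exists, so the fallback matters only for a treated subject without a pre-surgery sample.

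**What to change.** In SAP 11.8:

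- Define the between-arm any-visit positivity summary on the visits sampled in all arms: Months 1, 4, 8 and 12.
- Show Day 1 and Day 7 results, and an any-visit count on all samples, for the treated arms separately.
- Keep the treatment-emergent grouping in the within-arm safety tables on all available samples.
- State that the Day 1 fallback baseline applies only to assays sampled on Day 1.

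In SAP Appendix 2, reconcile the Visit 3 ELISpot mark with Protocol 10.3 and Table 3.

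The cost is SAP wording and one extra table row; no additional blood or visits are needed. The small downside is that an isolated Day 1 or Day 7 positive does not appear in the between-arm count, though it remains visible in the treated-arm display.

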5.2 Gene Therapy with Adeno-Associated Viral Vectors

Adeno-associated virus (AAV) is a parvovirus containing single stranded deoxyribonucleic acid (DNA). There are many different AAV subtypes, each with slightly different DNA sequences and capsid proteins. AAV serotype 2 (AAV2) is the vector to be used in this study. The wild type AAV2 genome lacks many of the viral sequences necessary for replication and packaging of viral particles and has evolved to become dependent on a helper virus (e.g. adenovirus or herpes simplex virus) for replication and spread from infected cells. In the absence of a helper virus, the AAV2 genome must remain dormant in the host cell which may have helped it to evolve to remain undetected by the eukaryotic immune system, although wild type AAV2 antibodies can be detected in about 30% of humans (Mingozzi 2007). Over time, the wild type AAV2 genome may become integrated into chromosome 19; however, this is not believed to occur in recombinant AAV because the integration mechanism involves part of the wild type sequence that is removed during cloning (Dutheil 2009).

The non-immunogenic features of AAV2 make it ideal for gene therapy. The principle is to remove the wild type AAV2 genome and replace it with a specific therapeutic transgene, thereby creating a "recombinant vector" which can deliver the therapeutic gene to diseased cells. The maximum size of the AAV2 genome is 4,700 base pairs and this must include the inverted terminal repeat sequences which remain at either end of the transgene (Lusby 1980). Hence the main drawback of AAV2 is the relatively small size of gene it can carry. At 1,900 base pairs however the REP1 complementary DNA (cDNA) coding sequence is well within this carrying capacity.

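### The ELISpot treatment-emergent rule counts conversion only, so a subject AAV2-positive at baseline can never be AAV2-emergent yet is tabulated with the non-emergent subjects

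*SAP*

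**What the plan says.** SAP 11.8 gives ADA and neutralising antibodies two routes to a treatment-emergent positive. One is conversion from negative to positive. The other is boosting: "A post-baseline result that has a titer greater than or equal to 4 times the baseline titer when the baseline result is positive", provided titres exist at both times.

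ELISpot has only the first route: "For ELISpot, the treatment-emergent positive for each analyte is defined as a post-baseline result that is positive when the baseline result is negative". The rule is repeated for the capsid analyte: "The treatment-emergent positive for AAV2 is defined as a post-baseline result that is positive when the baseline result is negative". The summaries then build upward from the analytes: "If any of the 3 REP1 analytes is treatment-emergent positive, it is a treatment-emergent positive for REP1", and "If either REP1 or AAV2 is treatment-emergent positive, it is a treatment-emergent positive for the overall treatment of BIIB111".

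The only stated ground for leaving a subject out of the emergent assessment is a missing or invalid baseline or post-baseline sample. Baseline positivity is neither an exclusion nor a category of its own.

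The part of SAP 11.8 on immunogenicity and safety then tabulates four outcomes: ocular inflammation, reduced-acuity and hypersensitivity adverse events, and eyes losing at least 15 letters at Month 12. It groups subjects in two ways, by baseline assay status and by treatment-emergent status. For ELISpot this is done overall, for REP1 and for AAV2. As printed, both arms of the second grouping describe subjects without an emergent positive; one is evidently meant to be subjects with one.

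Subject listings include "titer information (spot forming units (SFU) for ELISpot assay") where available.

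**The concern.** The SAP accepts boosting as treatment-emergent for antibodies and gives no reason for leaving it out for T cells. A subject with AAV2-reactive T cells before surgery whose spot count rises sharply after vector is classed the same way as a subject with no T-cell response at all.

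This matters because the emergent grouping is where immune response is set against ocular harm. Protocol 5.4 names loss of visual acuity as a potential risk whose cause was not definitively assigned to procedure or product. Protocol 9.8 gives corticosteroid partly because of possible immune responses to vector and transgene. If boosted responders carry extra risk and sit in the reference group, the reference risk is raised and any association looks weaker than it is.

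**Working it through.** **Step 1: who can never be emergent.** The SAP states no figure here to reproduce, so the rule was applied to all 16 baseline patterns of the four analytes (three REP1 pools and AAV2).

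| Summary | Baseline patterns that can never be emergent | Condition |
|---|---|---|
| AAV2 | 8 of 16 | AAV2 positive |
| REP1 | 2 of 16 | all three REP1 pools positive |
| Overall | 1 of 16 | all four analytes positive |

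These count patterns, not subjects; the patterns are not equally likely. In every other pattern, a boosted subject is non-emergent only if no baseline-negative component analyte converts.

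**Step 2: what the other planned tables add.**
- The positivity table in SAP 11.8 is split by baseline status. For AAV2 it gives positivity among baseline-negatives, which is the conversion rate with the right denominator. Among baseline-positives it is binary, so a stable result and a large rise look alike.
- The baseline-status grouping in the safety tables shows event rates for AAV2-positive-at-baseline subjects, but is not crossed with response after treatment.
- Spot counts appear only in listings. No planned table separates boosted from stable subjects.

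**Step 3: illustration of the dilution at AAV2 level.** Every input is an assumption. The documents give no ELISpot prevalence; the nearest figure, in Protocol 5.2, concerns antibodies: "wild type AAV2 antibodies can be detected in about 30% of humans". Let b be baseline positivity (10%, 20%, 30%), with half of baseline-positives boosting, conversion of 20% among baseline-negatives, event risk 0.40 in true responders (converters or boosters) and 0.10 in others. The true ratio is 0.40/0.10 = 4.0.

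Risk in the non-emergent group = [(1−b)(0.8)(0.10) + b(0.5×0.40 + 0.5×0.10)] / [1 − 0.2(1−b)].

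Share of true responders missed = 0.5b / [0.5b + 0.2(1−b)].

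| b | Non-emergent risk | Apparent ratio | Responders missed |
|---|---|---|---|
| 0.10 | 0.097/0.82 = 0.118 | 3.4 | 0.05/0.23 = 22% |
| 0.20 | 0.114/0.84 = 0.136 | 2.9 | 0.10/0.26 = 38% |
| 0.30 | 0.131/0.86 = 0.152 | 2.6 | 0.15/0.29 = 52% |

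**Step 4: milder assumptions.** Take 96 treated subjects (64 + 32), baseline positivity 5–30%, 25–50% of those boosting, 20% conversion, and risks 0.30 and 0.10 (true ratio 3.0, true difference 0.20).
- At 5% and 25%, about 1 boosted subject is misplaced: ratio 2.91, difference 0.197, 94% of responders captured.
- At 30% and 50%, about 14 are misplaced: ratio 2.22, difference 0.165, 48% captured.

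**Step 5: effect of a third group.** With AAV2-positive-at-baseline subjects set apart, the Step 3 comparison is converters at 0.40 against baseline-negative non-converters at 0.10, which returns 4.0. The third group has risk 0.5×0.40 + 0.5×0.10 = 0.25. No threshold is needed.

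**The case against.** A reader might infer that every subject boosted in any analyte falls into the non-emergent group in all three ELISpot summaries. The documents do not support that. Misplacement is unconditional only for AAV2; for REP1 and overall, conversion in another analyte still makes the subject emergent.

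A reader might also infer that the plan nowhere gives a clean response rate. It does in part, since the positivity table by baseline status yields AAV2 conversion among baseline-negatives. It does not supply boosting or correct the adverse-event comparison.

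The magnitude is open to more serious objection. Prevalence, boosting, conversion and risks are all assumed. The antibody figure cannot be read as ELISpot prevalence, and nothing in the documents says a recall response is expected or that boosters share the converters' risk. At the mild end the effect nearly vanishes. This objection stands against any claim about size, but not against the definitional gap.

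The tables are also descriptive (Protocol 13.7, SAP 11) and are run by treatment group. Under the Step 3 assumptions, boosted subjects number about 3 to 10 of 64 at high dose (64 × 0.5b) and 2 to 5 of 32 at low dose. No endpoint, error rate or stated decision rule depends on them. That stands, and limits the severity.

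Finally, paired spot counts are not guaranteed: Protocol 12.5.1 says selected samples may be analysed, and the listings carry values only where available. A fold threshold for spot counts would also need assay-precision data that the documents do not give.

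**Conclusion.** The point holds in limited form. The ELISpot rule lacks the boosting route that the antibody rule has. For AAV2, every baseline-positive subject with valid samples is non-emergent by definition, but stays in the denominator and in the evidently intended comparator. For REP1 and overall, this occurs only when no baseline-negative analyte converts, and emergence is impossible only when all component analytes are positive at baseline. The comparator itself is inferred, because the second safety grouping is misprinted.

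If boosted responses carry risk, the bias is toward no association. Its size cannot be derived from the documents; the ratios above are illustrations resting on assumed inputs. Severity is minor: descriptive safety tables only, although they concern a named risk of the product.

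**What to change.** Amend SAP 11.8 before database lock.

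1. **AAV2.** In the emergent table and the safety tables, report subjects AAV2-positive at baseline as a third group, outside both the emergent denominator and the non-emergent comparator.
2. **REP1 and overall.** Keep as emergent anyone who converts in any component analyte. Show non-converters with at least one baseline-positive component analyte separately. Remove from the denominator only subjects with every component analyte positive at baseline. Removing all baseline-positive subjects would discard people who can convert, or did, through another analyte.
3. **Wording.** Correct the second safety grouping so that it contrasts subjects with and without an emergent positive.
4. **Optional.** Where paired spot counts exist, add a fold-rise route for baseline-positive analytes, with the threshold set from assay precision before database lock. It should not simply be borrowed from the 4-fold titre rule.

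Items 1 to 3 need only SAP wording and a little programming on assay results the plan already uses. The price is small cells, particularly at low dose. The third group stops the misclassification but does not itself measure boosting; only item 4 does that.
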